## **4.2. Variable Definitions**

### **4.2.1. Body Mass Index**

Body mass index will be calculated as follows:

$$\text{Body mass index (kg/m}^2\text{)} = [\text{weight (kg)}] / [\text{height (m)}]^2.$$

### **4.2.2. Prior and Concomitant Medication**

Prior medication is defined as any nonstudy medication started before the first dose of ruxolitinib/placebo.

Concomitant medication is defined as any nonstudy medication that is started accordingly:

- Before the date of first administration of ruxolitinib/placebo and is ongoing throughout the study or ends on/after the date of first study drug administration.
- On/after the date of first administration of ruxolitinib/placebo and is ongoing or ends during the course of study.

A prior medication could also be classified as "both prior and concomitant medication" if the end date is on or after the first dose of ruxolitinib/placebo. In the listing, it will be indicated whether a medication is only prior, only concomitant, or both prior and concomitant.

For the purposes of analysis, all medications will be considered concomitant medications unless the medications can unequivocally be defined as not concomitant.

### **4.2.3. Mean Arterial Pressure**

The mean arterial pressure will be calculated as follows:

$$\text{Mean arterial pressure (mmHg)} = [\text{systolic blood pressure (mmHg)} + 2 \times \text{diastolic blood pressure (mmHg)}] / 3.$$

## **5. STATISTICAL METHODOLOGY**

### **5.1. General Methodology**

Unless otherwise noted, SAS® software (SAS Institute Inc, Cary, NC; v9 or later) will be used for the generation of all tables, graphs, and statistical analyses. Descriptive summaries for continuous variables will include but not be limited to the number of observations, mean, standard deviation, median, minimum, and maximum. Descriptive summaries for categorical variables will include the number and percentage of participants in each category.

### **5.2. Treatment Groups**

This is a randomized, double-blind, parallel treatment group design. Participants will be summarized by treatment groups.

### **5.3. Analysis Populations**

#### **5.3.1. All-Screened Population**

The all-screened population will include all participants who provided informed consent (written or verbal).

#### **5.3.2. Intent-to-Treat Population**

All participants who are randomized will constitute the ITT population. Treatment groups for this population will be defined according to the treatment assignment at the time of randomization regardless of the actual study drug the participant might take during his/her participation in the study.

The ITT population will be used for the summary of demographics, baseline characteristics, participant disposition, and analyses of all efficacy data.

#### **5.3.3. Per-Protocol Population**

The PP population comprises the subset of subjects in the ITT population who are compliant with requirements of the clinical study Protocol, including the following:

- Continued to meet all eligibility criteria on Study Day 1.
- Initiated correct randomized therapy within the Protocol-specified window.
- Did not significantly deviate from the Protocol in terms of missed study assessments, noncompliance with randomized therapy, or prohibited concomitant medications.

The PP population will be used in a supportive sensitivity analysis for the primary efficacy endpoint.

#### **5.3.4. Safety Population**

The safety population will include all participants who received at least 1 dose of ruxolitinib/placebo. Treatment groups for this population will be determined according to the actual treatment the participant received regardless of assigned study drug treatment.

All safety analyses will be conducted using the safety population.

## 6. BASELINE, EXPOSURE, AND DISPOSITION

[Appendix A](#) provides a list of data displays. Sample data displays are included in a separate document.

### 6.1. Demographics, Baseline Characteristics, and Disease History

#### 6.1.1. Demographics and Baseline Characteristics

The following demographics and baseline characteristics will be summarized for the ITT population: age, gender, race, ethnicity, weight, height, and BMI.

#### 6.1.2. Baseline Disease Characteristics and Disease History

The following baseline disease characteristics will be summarized for the ITT population: predefined coexisting disorders, baseline SOFA score, baseline COVID-19 9-point ordinal scale clinical status, baseline ARDS severity (severe [ $\text{PaO}_2/\text{FiO}_2 \leq 100$ ] vs mild/moderate [ $\text{PaO}_2/\text{FiO}_2 > 100$  and  $\leq 300$  mmHg]), ARDS severity at randomization, time (in hours) from start of mechanical ventilation to randomization, time (in days) from initial diagnosis to randomization, time (in days) from hospital admission to randomization, baseline CRP ( $\leq 100$  mg/L or  $> 100$  mg/L), baseline D-dimer ( $\leq 1000$  ng/mL or  $> 1000$  ng/mL), baseline ferritin ( $\leq 300$  ng/mL or  $> 300$  ng/mL), BMI at baseline ( $\geq 30$  or  $< 30$ ), prior or concomitant remdesivir, prior or concomitant convalescent plasma, prior or concomitant corticosteroid, concomitant anti-coagulant, prior biologic, prior or concomitant neutralizing antibodies, and prior or concomitant corticosteroid with prior or concomitant remdesivir.

Time from initial diagnosis will be calculated as follows:

$$\text{Time since diagnosis (days)} = (\text{date of randomization} - \text{date of diagnosis} + 1).$$

Time from start of mechanical ventilation will be calculated as follows:

$$\text{Time from start of mechanical ventilation (hours)} = (\text{date and time of randomization} - \text{date and time of intubation}).$$

Time from hospital admission to randomization will be calculated as follows:

$$\text{Time from hospital admission (days)} = (\text{date of randomization} - \text{date of hospital admission} + 1).$$

#### 6.1.3. Medical History

For participants in the ITT population, medical history will be summarized by assigned treatment group. This summation will include the number and percentage of participants with significant medical history for each body system/organ class as documented on the eCRF.

## 6.2. Disposition of Participant

The number and percentage of participants, who were treated, who were ongoing with study treatment, who completed study treatment, who discontinued study treatment with a primary reason for discontinuation, who were still in the study, who completed the study, and who withdrew from the study with a primary reason for withdrawal will be summarized for the ITT population. The number of participants randomized by country and/or site will also be provided by treatment group.

## 6.3. Protocol Deviations

Protocol deviations recorded on the eCRF will be summarized and listed.

## 6.4. Exposure

For participants in the safety population, exposure to ruxolitinib/placebo will be summarized descriptively as the following:

- **Duration of treatment with ruxolitinib/placebo (days):** date of last dose of ruxolitinib/placebo – date of first dose of ruxolitinib/placebo + 1.
- **Average daily dose of ruxolitinib/placebo (mg/day):** total actual ruxolitinib/placebo dose taken (mg) / duration of treatment with ruxolitinib/placebo (days).
- **Ruxolitinib/placebo dose modifications:** number of participants who had ruxolitinib/placebo dose reduction, escalation, and interruption.

In addition, total daily dose of ruxolitinib/placebo dosing will be summarized by day.

## 6.5. Study Drug Compliance

As ruxolitinib/placebo dosing will be captured on the appropriate exposure eCRF, overall compliance (%) will be calculated for all participants as follows:

$$\text{Compliance (\%)} = 100 \times [\text{total dose actually taken}] / [\text{total prescribed dose}].$$

The total prescribed dose is defined as the sum of the doses prescribed by the investigator accounting for dose modifications.

## 6.6. Prior and Concomitant Medication

Prior medications and concomitant medications will be coded using the WHO Drug Dictionary. The number and percentage of participants in the ITT for each prior and concomitant medication will be summarized by WHO drug class and WHO drug PT.

## 7. EFFICACY

[Appendix A](#) provides a list of data displays. Sample data displays are included in a separate document.

### 7.1. General Considerations

Unless otherwise stated, the strata identified in the randomization process will be used in all efficacy analyses. For statistical analyses of the primary and secondary endpoints, separate models will be fit for the ruxolitinib 5 mg BID versus placebo and ruxolitinib 15 mg BID versus placebo comparisons.

### 7.2. Efficacy Hypotheses

The primary hypothesis is that ruxolitinib in combination with SoC will reduce 28-day mortality, as measured by odds ratio, compared with placebo in combination with SoC in participants with COVID-19–associated ARDS who require mechanical ventilation. The hypothesis of the study are as follows:

- $H_0$  (null hypothesis):  $\theta_{RUX05} = \theta_{RUX15} = \theta_{PLB}$
- $H_A$ (alternative hypothesis):  $\theta_{RUX15} < \theta_{PLB}$  OR ( $\theta_{RUX05} < \theta_{PLB}$  and  $\theta_{RUX15} < \theta_{PLB}$ )

The 5 mg BID hypothesis will only be tested if the 15 mg BID hypothesis is significant. In the event that both individual null hypotheses are rejected, then a test for a difference between the 5 mg BID and 15 mg BID treatment groups will be performed for the 28-day mortality endpoint. The hypothesis for this test is:

- $H_0$  (null hypothesis):  $\theta_{RUX05} = \theta_{RUX15}$
- $H_A$ (alternative hypothesis):  $\theta_{RUX15} \neq \theta_{RUX05}$

### 7.3. Analysis of the Primary Efficacy Parameter

#### 7.3.1. Primary Efficacy Analysis

The primary endpoint, 28-day mortality, will be tested using a logistic regression mixed model including treatment group (specific ruxolitinib treatment group vs placebo) and ARDS severity (severe vs mild/moderate) as fixed covariates and investigational site as a random (intercept) effect. The estimation technique for the model fit will use the residual pseudo-likelihood with a subject-specific expansion ([SAS Institute 2013](#)) approach and will be implemented in the SAS GLIMMIX procedure. If the model is not estimable due to convergence issues, a fixed effects logistic regression will be performed instead, excluding investigational site from the model. The Wald test for the treatment regression coefficient will test the primary endpoint.

An estimate and 95% CI for the difference in proportions for 28-day mortality for the 2 treatment groups will be provided. The estimate will be based on the logistic regression model ([Ge et al 2011](#)) using an average of the difference between the 2 levels of the fixed factor (ARDS severity) weighted for the proportion of the study population within each of the 2 levels

of the fixed factor. The delta method will be used to derive the variance estimate, based on the functional form of the estimate  $\gamma^T g(\underline{b})$  using  $\gamma = (\gamma_1, \gamma_2)$  where

- $\gamma_1$  is the proportion of participants in the  $b_2 = 0$
- $\gamma_2$  is the proportion of participants in the  $b_2 = 1$

$\underline{b}$  is the vector of the logistic regression coefficients, and

$$g(\underline{b}) = \frac{1/1 + \exp(\underline{\gamma}^T \underline{b}_0 - b_1) - 1/1 + \exp(\underline{\gamma}^T \underline{b}_0)}{1/1 + \exp(\underline{\gamma}^T \underline{b}_0 - b_1 - b_2) - 1/1 + \exp(\underline{\gamma}^T \underline{b}_0 - b_2)} .$$

Point estimates and 95% CIs will also be provided for the model-based mortality rates using the delta method.

Participants who are lost to follow-up before Day 29 will not be evaluable for this endpoint. As the participants begin the study intubated, those who remain hospitalized are unlikely to be lost to follow-up, but reasonable efforts will be made to track down missing participants.

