According to the WHO interim guidance of 13 MAR 2020 on the clinical management of severe acute respiratory infection when COVID-19 is suspected, "older age and comorbid disease have been reported as risk factors for death, and recent multivariable analysis confirmed older age, higher SOFA score and d-dimer > 1 μ g/L on admission were associated with higher mortality" (WHO 2020b). The same study quoted by the WHO also noted that the median duration of viral RNA detection was 20.0 days (interquartile range 17.0–24.0) in survivors, but SARS-CoV-2 was detectable until death in nonsurvivors. The longest observed duration of viral shedding in survivors was 37 days (Huang et al 2020, Zhou et al 2020).

There are sparse data on the clinical presentation of COVID-19 in specific populations, such as children and pregnant women. In children with COVID-19, the symptoms are usually less severe than in adults and present mainly with cough and fever, and coinfection has been

observed (Cai et al 2020, Xia et al 2020). Relatively few cases have been reported of infants with confirmed COVID-19, and they experienced mild illness (Wei et al 2020).

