9.3.4. Sequential Organ Failure Assessment Score

The SOFA score (Appendix C) is a scoring system to determine the extent of a person's organ function or rate of failure. The score is based on 6 different scores, 1 each for the respiratory, cardiovascular, hepatic, coagulation, renal, and neurological systems. The screening/Day 1 assessment should be based on data collected closest to (but also prior to) randomization. Each subsequent day should use the worst value for each parameter in the preceding 24-hour period.

At each required timepoint, the SOFA score will be calculated by the investigative site and recorded in the appropriate eCRF. The SOFA score assessments are no longer required after discharge from the ICU.

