9.4.3.3. Inflammatory Markers

- Ferritin
- CRP
- D-dimer
- Procalcitonin
- IL-6 at sites where feasible

Samples will be collected at the timepoints defined in Table 3. If a given test is not available locally, this should be documented on the eCRF.

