**Table 2: Simulation Estimates for Power and Type 1 Error for Various Mortality Rates**

Mortality Rates			Probability to Reject H 0 for		
PLB	5 mg BID	15 mg BID	5 mg BID	15 mg BID	Either RUX
60%	60%	60%	0.015	0.016	0.027
60%	60%	40%	0.012	0.873	0.873
60%	50%	40%	0.268	0.865	0.866
60%	40%	40%	0.868	0.872	0.940
60%	40%	30%	0.861	0.998	0.998

Note: For the simulation, investigational site was drawn from an integer uniform distribution (1, 2, ..., 10) and probability (ARDS severe) = 0.5, fitting a mixed logistic regression model with no direct effects for the ARDS severity or site.

Enrollment was halted and SAP Amendment 3 removed the interim analysis. The final analysis will be performed using all randomized participants enrolled at the time of SAP Amendment 3, which is 211 participants.

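### The primary mortality model leaves out age and baseline SOFA, which the protocol itself cites as prognostic, and so gives up some power in an analysis cut to 211 participants

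*SAP*

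**What the plan says.** SAP 7.3.1 tests 28-day mortality with a mixed logistic model "including treatment group (specific ruxolitinib treatment group vs placebo) and ARDS severity (severe vs mild/moderate) as fixed covariates" and a random intercept for site. If the model does not converge, site is dropped. The accompanying risk difference averages over the two ARDS severity levels only.

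SAP Table 3 lists the supportive models. One adds gender, which the protocol had in its primary model and the SAP moved to a sensitivity analysis (SAP 11.1.1). No row contains age or SOFA. Age is a subgroup factor in SAP 7.3.2.

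Protocol 2.1 cites guidance on risk factors for death in which "recent multivariable analysis confirmed older age, higher SOFA score and d-dimer" above a threshold at admission were linked to mortality. Age is among the ITT baseline variables in SAP 6.1.1 ("age, gender, race, ethnicity, weight, height, and BMI"). SOFA is among those in SAP 6.1.2 ("predefined coexisting disorders, baseline SOFA score, baseline COVID-19 9-point ordinal scale clinical status"). Protocol 9.3.4 fixes the timing of SOFA: "The screening/Day 1 assessment should be based on data collected closest to (but also prior to) randomization".

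On sample size, SAP 3.3 states: "The final analysis will be performed using all randomized participants enrolled at the time of SAP Amendment 3, which is 211 participants".

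**The concern.** In logistic regression, leaving out a covariate that predicts the outcome pulls the treatment coefficient toward zero. Putting it in raises the standard error, but it raises the coefficient by more, so the Wald statistic grows on average. The sponsor therefore appears to pass over information that its own background section calls prognostic and that is already collected, while giving a supportive model to gender, which the quoted sentence does not name.

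This matters more since SAP Amendment 3. Each comparison was planned with 100 placebo and 200 ruxolitinib participants and now has well under half of that. SAP 3.2 tests the two doses in fixed sequence, 15 mg BID first, so a miss on 15 mg also ends testing of 5 mg. Power on the first test counts for both doses.

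D-dimer is named in the same sentence but is a weaker candidate, because Protocol 9.4.3.3 allows for its absence: "If a given test is not available locally, this should be documented on the eCRF". Comorbidity has no defined score.

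**Working it through.** **The plan's own figure.** SAP 3.3 gives about 83% power for 100 versus 200 participants, 60% versus 40% mortality, 1-sided alpha 0.01436968. Using power = Φ[(0.2 − z·SE0)/SE1]:

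- Pooled mortality = (100×0.6 + 200×0.4)/300 = 0.4667.
- SE0 = √[0.4667×0.5333×(1/100+1/200)] = 0.0611; SE1 = √[0.24×(1/100+1/200)] = 0.0600.
- With z = 2.187, power = Φ(1.106) = 86.6%, in line with the simulated 0.861 to 0.873 in SAP Table 2.
- Fisher's exact test gives 83.2% and the pooled test with continuity correction 83.7%, so the stated 83% reproduces on a more conservative test.

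**Power at 211.** Arm sizes are not given. Allocation 2:2:1 implies 211/5 ≈ 42 placebo and 84 per dose. SAP 3.2 now tests at 1-sided 0.025.

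- SE0 = √[0.4667×0.5333×(1/42+1/84)] = 0.0943; SE1 = √[0.24×(1/42+1/84)] = 0.0926.
- Power = Φ[(0.2 − 1.96×0.0943)/0.0926] = Φ(0.164) = 56.5%.
- The same formula for 100 versus 200 at 0.025 gives Φ(1.337) = 90.9% (0.915 in simulation).

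**Gain from adjustment.** The test is the logistic Wald test at 1-sided 0.025 with 42 versus 84 participants and 20,000 replicates. Intercepts are calibrated so that marginal mortality is 60% versus 40%. Half the participants are severe, with a severity odds ratio of 1.3 to 1.5. SOFA and severity have correlation 0.3, because the SOFA respiratory component uses PaO2/FiO2. The documents give no effect sizes for age or SOFA, so the odds ratios per SD are assumed.

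| OR per SD (age, SOFA) | Power, severity only | Power, plus age and SOFA | Effective-N ratio |
|---|---|---|---|
| 1.0, 1.0 (none) | 0.568 | 0.567 | 1.00 |
| 1.3, 1.3 (weak) | 0.569 | 0.579 | 1.02 |
| 1.5, 1.3 | 0.570 | 0.592 | 1.05 |
| 1.8, 1.5 (moderate) | 0.573 | 0.613 | 1.10 |
| 2.2, 1.7 (strong) | 0.574 | 0.640 | 1.17 |
| 2.5, 2.2 (very strong) | 0.569 | 0.667 | 1.25 |

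The last column is [(1.96 + z_adj)/(1.96 + z_unadj)]², where each z is the normal quantile of the power. For the moderate row, [(1.96 + 0.287)/(1.96 + 0.184)]² = 1.10. Type I error, at 60% in both arms, is 0.021 to 0.024 without adjustment and 0.022 to 0.026 with it.

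**Robustness.**

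- Age and SOFA independent of severity, severity odds ratio 1.5: odds ratios of 1.5 each give 0.567 versus 0.593, 2.0 each 0.567 versus 0.639, and 2.5 and 2.0 give 0.565 versus 0.660.
- Random site intercept by residual pseudo-likelihood (10 sites as in the SAP Table 2 note, assumed site SD 0.5 on the logit scale, 3,000 replicates): none 0.583 versus 0.578, weak 0.545 versus 0.567, moderate 0.576 versus 0.605, strong 0.585 versus 0.641. Type I error is 0.022 to 0.030 without adjustment and 0.020 to 0.027 with it. Both models converged in every power run.
- 10% missing SOFA filled with a median: moderate 0.567 versus 0.608, strong 0.571 versus 0.634. Adjusted type I error is 0.024 to 0.027.

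**Scale.** Stopping at 211 costs about 0.915 − 0.574 = 34 points. Adjustment regains 0.579 − 0.569 = 1 point (weak) to 0.640 − 0.574 = 7 points (strong).

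**The case against.** The planned analysis is not wrong. SAP 7.1 says that the randomization strata will be used in efficacy analyses. Those strata are ARDS severity and site, both are in the model, and stopping there is an accepted choice. This stands, and the point is one of efficiency only.

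The size of the gain is assumed, and the low end is plausible. The cited associations were measured at admission, not in ventilated patients. Eligibility narrows the SOFA range: everyone is intubated with PaO2/FiO2 of 300 mmHg or less, while dialysis, very low platelet counts and expected early death are excluded. The neurological component is the Glasgow coma score, and the SOFA appendix has no rule for sedated participants. The simulations do not model this noise or range restriction. This also stands, but it moves the gain toward the bottom of the range and not below it: with no prognostic effect, the two models have nearly the same power and type I error.

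The choice of covariates is partly a judgement. D-dimer is set aside for possible missingness, while missing SOFA would be imputed.

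The change has a price. SAP 11.2.1 lists the risk-difference estimator among changes that followed FDA comments, and the primary odds ratio would become conditional on more covariates. Standardization generalizes that estimator: with severity as the only covariate, averaging predicted differences over participants is the same as weighting by the severity proportions. The shift in the odds ratio is real and has to be explained.

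A supportive row in Table 3 alone would be the milder remedy. It would address robustness but leave primary power unchanged.

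**Conclusion.** The concern holds as a recommended improvement, not as an error in the test. The primary model omits two baseline variables that the protocol cites as prognostic and that are scheduled before treatment. At about 42 versus 84 participants, including them would add 0 to about 10 points to a power of about 57%, equivalent to 0% to about 25% more participants. Adjustment recovers only a small part of the power lost by stopping at 211.

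This rests on the planned 60% versus 40% mortality, an arm split derived from 2:2:1, complete Day 29 status, and assumed prognostic strengths. The direction of the result is firm. Its size is not.

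**What to change.** Amend the SAP before unblinding:

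1. In SAP 7.3.1, its convergence fallback and Table 3, add age and pre-randomization total SOFA, both continuous, as fixed covariates alongside treatment, ARDS severity and random site.
2. Replace the two-level risk-difference formula with standardization: for each participant take predicted risk under ruxolitinib minus predicted risk under placebo, average over the observed covariates, and use a matching delta-method variance.
3. Fill missing baseline SOFA with a single treatment-blind value, such as the pooled median within ARDS severity stratum, so that nobody is dropped.
4. Keep the current model of severity and site as a named sensitivity analysis.

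The cost is an amendment, a re-derived and re-programmed estimator and variance, and an imputation rule. The reported odds ratio also changes meaning: the simulated median is 0.43 with severity only, 0.39 with moderate and 0.36 with strong covariates, for the same marginal benefit. The report should say so and give the standardized risk difference beside it.

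The documents do not show whether there is still time. Enrollment has halted, and the date printed for SAP Amendment 3 precedes that of the original SAP. If treatment codes have already been opened, the adjusted model can be added only as a supportive analysis labelled post hoc.

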### 7.3.3. Sensitivity and Supportive Analyses for Primary Endpoint

A sensitivity analysis will be conducted in the ITT population, in which nonevaluable participants will be treated as deaths. The primary endpoint will be analyzed using the PP population as a sensitivity analysis to the ITT analysis. In addition, a tipping point analysis will be performed to measure the robustness of the treatment effect under assumptions for participant dropout. The tipping point analysis will use an unstratified 2-sample test of proportion, modifying dropouts within the compared ruxolitinib treatment group as having died and placebo participants as having lived to determine if and at what point in this imputation a statistically significant treatment effect under the base assumptions will lose statistical significance.

Analyses related to the primary endpoints are delineated in [Table 3](#).

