**Table 3: Primary and Sensitivity Analyses of Primary Endpoints**

Endpoint	Statistical Method	Analysis Population	Primary (P) or Supportive (S)
Proportion of participants who have died due to any cause through Study Day 29.	Logistic regression with treatment group and ARDS severity (severe vs mild/moderate) as fixed covariates, and investigational site as a random effect. Wald test for treatment group regression coefficient = 0.	ITT	P
	Estimation: Odds-ratio for treatment effect and associated 95% CI.	PP	S
	Logistic regression with treatment group and ARDS severity (severe vs mild/moderate) as fixed covariates, and investigational site as a random effect, treating participants who are lost to follow-up before Day 29 as deaths.	ITT	S
	Logistic regression with treatment group and ARDS severity (severe vs mild/moderate) as fixed covariates, and investigational site as a random effect using actual PaO 2 /FiO 2 at Day 1 (as entered into eCRF).	ITT	S
	Logistic regression with treatment group, ARDS severity (severe vs mild/moderate), and gender (male or female) as fixed covariates, and investigational site as a random effect. Wald test for treatment group regression coefficient = 0.	ITT	S

The 28-day mortality rates and participants lost to follow-up in the placebo group will be compared by the placebo image assigned (5 mg BID and 15 mg BID) to determine if the rate is consistent across the 2 treatment images. Statistical comparisons between the 2 images will be performed using a Fisher's exact test in all placebo-assigned participants and within ARDS

severity subgroup. Additional endpoints may also be compared within placebo-assigned participants by treatment image.

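### The primary ITT mortality analysis drops participants lost before Day 29, probably mostly people discharged alive, and no listed analysis uses last known status in both arms

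*SAP*

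**What the plan says.** SAP 5.3.2 defines the population: "All participants who are randomized will constitute the ITT population". It assigns that population to all efficacy analyses. SAP 7.3.1 then removes part of it from the primary test: "Participants who are lost to follow-up before Day 29 will not be evaluable for this endpoint". The next sentence gives the reassurance that, because participants start the study intubated, "those who remain hospitalized are unlikely to be lost to follow-up", and promises reasonable efforts to trace the missing.

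SAP 7.3.3 adds two checks on missing status:
- An ITT sensitivity analysis in which "nonevaluable participants will be treated as deaths". Table 3 repeats it as a supportive analysis, "treating participants who are lost to follow-up before Day 29 as deaths".
- A tipping-point analysis with an unstratified two-sample test, "modifying dropouts within the compared ruxolitinib treatment group as having died and placebo participants as having lived", to find where a significant effect would be lost.

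Protocol 3.1 names study discontinuation other than by death as an intercurrent event but states no strategy for it. Protocol Table 10 has a supportive Cox and Kaplan-Meier analysis of survival to Day 29. Neither SAP Table 3 nor SAP Appendix A contains it.

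**The concern.** Under this rule, inclusion depends on the outcome. A participant known to have died is always counted, while one who left hospital alive and could not be reached is not. SAP 7.4.2 and 7.4.3.1 both write rules for participants released from hospital and then lost, so this kind of loss was foreseen.

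SAP 7.3.1 promises model-based mortality rates and a risk difference as well as the OR. If most of those lost are alive, the rates are too high in every arm. If the share of survivors lost differs by arm, the OR and the risk difference are biased too. The coded-as-deaths analysis gives the same people the less likely outcome, so it may not show the reader which way the primary result is wrong.

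**Working it through.** **Inputs.** Mortality of 60% on placebo and 40% on ruxolitinib, with 100 vs 200 participants (Protocol 12.1, SAP 3.3). One-sided alpha is 0.01436968 in the sample-size text and 0.025 in SAP 3.2. Final N is 211 (SAP 3.3), which at 2:2:1 is about 42 placebo and 84 per ruxolitinib arm. The documents give no loss rate, so loss among survivors is assumed between 0% and 20%, with everyone lost truly alive.

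**The plan's own figure.** Pooled proportion (60 + 80)/300 = 0.4667. Null SE = √(0.4667 × 0.5333 × 0.015) = 0.0611; alternative SE = √(0.24/100 + 0.24/200) = 0.060; critical z = 2.187.
- Power = Φ((0.20 − 2.187 × 0.0611)/0.060) = 86.6%, in line with the simulated 0.868 and 0.872.
- A continuity correction of 0.0075 gives 83.7%, in line with the stated 83%.

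The inputs are confirmed, but neither calculation allows for loss.

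**Formulas.** Let p be true mortality and l the share of survivors lost.
- Deleted: p / (p + (1 − p)(1 − l)). The odds are the true odds divided by (1 − l), so OR(deleted) = true OR × (1 − l placebo)/(1 − l ruxolitinib). Equal loss leaves the OR unchanged.
- Coded dead: p + (1 − p)l.

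**Results** (truth: 60% vs 40%, difference 20 points, OR 0.444).

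| Survivors lost, placebo / ruxolitinib | Deleted | Coded dead |
|---|---|---|
| 10% / 10% | 62.5 vs 42.6%, diff 19.9, OR 0.444 | 64 vs 46%, diff 18.0, OR 0.479 |
| 5% / 15% | 61.2 vs 44.0%, diff 17.3, OR 0.497 | 62 vs 49%, diff 13.0, OR 0.589 |
| 15% / 5% | 63.8 vs 41.2%, diff 22.6, OR 0.398 | 66 vs 43%, diff 23.0, OR 0.389 |

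Example, 5%/15% deleted: 0.444 × 0.95/0.85 = 0.497.

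**Does coding as dead bracket the truth?** In both unequal rows it moves further from 0.444 on the same side as deletion. The ratio OR(coded dead)/OR(deleted) is (1 + l ruxolitinib/0.667)/(1 + l placebo/1.5), where 0.667 and 1.5 are the true odds. So the same-direction shift holds for any excess loss on ruxolitinib, and for placebo loss above 1.5/0.667 = 2.25 times the ruxolitinib loss. Between 1 and 2.25 times, coding as dead pulls back toward the null. At 10%/8% the two analyses straddle the truth (0.435 and 0.457); at 10%/5% they do not (0.421 and 0.424). With no true effect the odds are equal, so any difference in loss pushes both analyses the same way.

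**At the actual size.** Simulation of 42 vs 84 (200,000 trials, unadjusted Wald test on the log OR, one-sided 0.025):
- 60% vs 40%: power 57% without loss. With 10% lost in both arms, 54% deleted and 48% coded dead. With 5% placebo and 10% ruxolitinib lost, 49% and 40%.
- No effect (60% in both), 15% placebo and 5% ruxolitinib lost: rejection 4.3% deleted, 5.8% coded dead, 1.4% at the tipping-point extreme, against 2.4% with status known.

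**In people.** Expected placebo survivors are 42 × 0.4 = 16.8, so 5% to 15% loss is about 1 to 3 participants. One lost moves placebo mortality from 60% to 25.2/41 = 61.5% if deleted, or 26.2/42 = 62.4% if coded dead.

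**The case against.** The strongest reply is that losses will be few and a stress test is already planned. Discharged participants are called daily for the ordinal scale, which includes death (Protocol 9 and 9.3.1). Stopping treatment is not study withdrawal (Protocol 10.1.1). Loss is declared only after repeated attempts at contact (Protocol 10.1.4). The safety contact 28 ± 3 days after the last dose falls after Day 29 for anyone completing 14 days of treatment, so Day 29 survival could be learned later. This stands as a limit on size: if under 5% of survivors are lost equally, little changes.

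A reader might infer that the SAP has no defence against a false positive from heavier placebo loss. The tipping-point analysis is that defence, and the 1.4% rejection rate above shows it works. But it is triggered only by a significant result, so it says nothing after a null one, and it yields no corrected estimate.

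A reader might also infer that deletion favours ruxolitinib. An effective drug that discharges people earlier exposes more of that arm to loss, which pulls the OR toward the null. The opposite bias needs heavier loss on placebo, and the documents give no reason to expect that.

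Finally, treating a discharged-then-lost participant as alive is itself an assumption. That stands, and is why imputation is preferable to that single rule.

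**Conclusion.** The point holds in limited form. The primary analysis labelled ITT is complete-case, and the rule favours dropping survivors. Under the assumed losses, reported mortality rises by about 1 to 5 points (equal loss of 5% gives 61.2% vs 41.2%; 20% gives 65.2% vs 45.5%). The risk difference hardly moves when loss is equal (19.9 against 20 points at 10%) and shifts by about 3 points at 5% vs 15%. The OR is biased only under unequal loss. The coded-as-deaths analysis cannot be relied on to bracket the truth.

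Three stronger readings go beyond the text. The SAP does not itself say that losses will be discharged survivors: it says only that loss in hospital is unlikely, consent can be withdrawn in hospital (Protocol 10.1.3), and Day 29 status after discharge is unknown. It does not rank the coded-as-deaths analysis above the others. It makes no claim that loss will be equal across arms.

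All sizes rest on assumed loss rates and on those lost being alive; later deaths among them would shrink the bias. The point warrants a change to the plan but does not invalidate the trial.

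**What to change.** Keep all randomized participants in the 28-day mortality analysis by multiply imputing missing Day 29 status from arm, ARDS severity and last known status (in hospital or discharged alive, and the day).

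At minimum, do one of the following:
- add an ITT analysis using last known status in both arms, with participants discharged alive and then lost counted as alive; or
- restore the protocol's supportive Cox and Kaplan-Meier survival analysis, censoring at the date last known alive.

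Keep the coded-as-deaths and tipping-point analyses as stress tests. Report losses by arm and by discharge status, so the reader can see whether the issue has any size.

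The cost is SAP text and modest programming. Daily clinical status and hospital-free days are already collected, and SAP 4.1.5 already uses a last-known-alive date. The price is an explicit assumption about status after discharge, which should be stated in the SAP.
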